9.5 Unmasking/Unblinding Procedures

Unblinding may only occur for emergency purposes which would affect clinical care. Investigators should note that the occurrence of a serious adverse event or progressive disease should not routinely precipitate the immediate unblinding. If unblinding is necessary for the treatment of a subject for a serious adverse event, every attempt should be made to contact the Principal Investigator (PI) prior to unblinding. If this is not feasible, then the Principal Investigator must be contacted within 24 hours of unblinding.

9.6 Medical Monitoring

It is the responsibility of the Principal Investigator to oversee the safety of the study at his/her site. This safety monitoring will include careful assessment and appropriate reporting of adverse events as noted above, as well as the construction and implementation of a site data and safety-monitoring plan. Medical monitoring will include a regular assessment of the number and type of serious adverse events.

9.6.1 Internal Data and Safety Monitoring Board

The principal investigator, co-investigators and study coordinators are responsible for safety monitoring. Subjects who develop adverse side effects that are assessed as being probably related to letrozole by the principal investigator will stop the study.

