4.6 Early Withdrawal of Subjects

4.6.1 When and How to Withdraw Subjects

A subject may be withdrawn from the study prior to that subject completing all of the study related procedures for the following reasons.

- Unanticipated adverse effects that are possibly or probably related to the study drug
- patients who miss more than 20% of doses or are not adherent to protocol requirements.
- Disease progression
- Subject decision to withdraw from the study (withdrawal of consent)
- Liver transplantation

Subjects who withdraw from the study for safety concerns or disease progression will be included in the primary analysis (safety and tolerability). As this is a short-term study, there will be no specific clinical follow-up for subjects withdrawn from the study.

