4.6.2 Data Collection and Follow-up for Withdrawn Subjects

Even though a subject has withdrawn from the study, it may be important to collect some follow-up or survival data on such subjects throughout the protocol defined follow-up period. Such data is important to the integrity of the final study analysis since early withdrawal could be related to the safety profile of the study drug in this population. If a subject withdraws consent to participate in the study, for subject safety reasons, attempts will be made to obtain permission to collect follow up information whenever possible.

5 Study Drug

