8.4.5 Missing Data and Dropouts

We will attempt to minimize missing data; however we have planned for its occurrence. For subjects lost to follow-up, we will use all of the information available until the end of follow-up. This protocol will continue to be followed and test procedures performed as prescribed even if a subject drops out of the therapeutic portion of the study. That is, if a subject decides that he/she does not wish to continue taking the study drug, the subject will stop the investigational treatment, but will still be strongly encouraged to continue to follow up with the study personnel for all scheduled study procedures (e.g., phlebotomy, echocardiography), so that missing data (and assumptions regarding these data) will be minimized.

For the primary end point, we will perform an analysis of completers only. We will also perform additional sensitivity analyses using imputation to assess the impact of missing data for the primary and secondary end points.

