9.4 Subject Withdrawal

A subject has the right to withdraw from the study entirely at any time for any reason without prejudice to future medical care by the investigator or other physician. The investigator also has

the right to withdraw subjects from the study in the event of concurrent illness, AEs, or other reasons deemed to be in the subject's best interest.

Subjects **must be withdrawn** from the trial (treatment and procedures) for the following reasons:

- Subject withdraws consent for study treatment and study procedures. A subject must be removed from the trial at his/her own request. At any time during the trial and without giving reasons, a subject may decline to participate further. The subject will not suffer any disadvantage as a result.
- Death.

Any subject removed from the trial will remain under medical supervision until discharge or transfer is medically acceptable.

In all cases, the reason for withdrawal must be recorded in the CRF and in the subject's medical records.

In order to preserve the integrity of the intention-to-treat analysis, even if the subject is withdrawn from the treatment portion of the protocol (either due to subject, physician, or investigator decision), it is imperative to continue with the scheduled follow-up assessments both for the safety of the subject and for completeness of data collection. This will be explained to potential subjects at the time of informed consent. The importance of compliance with study visits will be reinforced throughout the trial. If the treatment is permanently withdrawn, the subject will return to the center for safety assessment (history, physical examination, and clinical laboratories, if necessary).

In the event of clinical worsening, subjects will be continued on their assigned study medication. There is no evidence that the medication under study is effective in subjects with HPS, so that there is neither reason to unmask the study therapy nor to initiate treatment with sorafenib in such subjects.

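### Section 9.6.1 takes subjects with a probably related side effect out of the study, while 9.4 and 8.4.5 keep them in scheduled assessments; read literally, the month-6 AaPO2 can be lost

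*Combined protocol and SAP*

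**What the plan says.** Two sets of statements cover a subject who has a drug-related side effect.

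**Text that takes the subject out of the study**
- Section 9.6.1 is mandatory: "Subjects who develop adverse side effects that are assessed as being probably related to letrozole by the principal investigator will stop the study". It sets no severity threshold and does not separate the drug from the assessments.
- Section 4.6.1 is permissive: "A subject may be withdrawn from the study prior to that subject completing all of the study related procedures for the following reasons". Its adverse-effect reason is limited to unanticipated effects, and it covers possibly as well as probably related ones. It then says "there will be no specific clinical follow-up for subjects withdrawn from the study".
- Section 4.6.2 leaves some room, saying "it may be important to collect some follow-up or survival data on such subjects throughout the protocol defined follow-up period", but it does not name the ABG.

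**Text that keeps the subject in the study**
- Section 9.4 lists only withdrawal of consent and death as reasons for compulsory withdrawal from both treatment and procedures. For subjects taken off treatment ("either due to subject, physician, or investigator decision"), it says "it is imperative to continue with the scheduled follow-up assessments both for the safety of the subject and for completeness of data collection", and gives the integrity of the intention-to-treat analysis as the reason.
- Section 8.4.5 wants "test procedures performed as prescribed even if a subject drops out of the therapeutic portion of the study".

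**Analysis text**
- Sections 8.4.1 and 8.6 state intent-to-treat.
- Section 8.4.5 analyses the primary endpoint in completers, with imputation as a sensitivity analysis.
- Section 4.6.1 says that subjects withdrawn for safety or progression "will be included in the primary analysis (safety and tolerability"). The primary analysis in 8.4.3, however, is the AaPO2 comparison, so this does not say whether they stay in it.

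**The concern.** A coordinator who works from 9.6.1 and 4.6.1 could reasonably cancel the month-6 visit. One who works from 9.4 would keep it. With two sites, practice could also differ between them.

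The conflict reaches the primary endpoint. A subject without a month-6 ABG has no change score and leaves the primary t-test. The trigger is an adverse effect judged drug-related, so the loss may depend on assignment, and the comparison would then no longer be of the groups as randomised. The principal investigator is masked (5.7), so placebo subjects can be stopped too, but masking does not make the stop rates equal.

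The imputation analyses in 8.4.5 and the longitudinal models in 8.4.3 (for secondary outcomes, able to use the month-3 ABG) soften the effect. They do not put the subject back into the primary test.

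**Working it through.** **Step 1. Can the text be reconciled?**

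| Question | 9.6.1 with 4.6.1, read literally | 9.4 with 8.4.5 |
|---|---|---|
| Does a probably related side effect end study participation? | Yes, mandatory in 9.6.1 | No; only consent withdrawal or death does so compulsorily |
| Are scheduled assessments done afterwards? | None specified (4.6.1); some data may be useful (4.6.2) | Yes |
| Is the month-6 ABG obtained? | Not assured | Yes, as scheduled |
| Is the subject in the primary t-test? | No, if the ABG is missing | Yes |

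Section 8.4.5 speaks explicitly of stopping the investigational treatment. Section 9.6.1 does not, and nothing gives 9.4 precedence.

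**Step 2. Reproduce the plan's power.** Inputs: 10 per arm (Study Summary), SD of change about 10 mmHg and difference 13.2 mmHg (8.2), two-sided 0.05 (8.4.1), two-sample t-test (8.4.3).

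Noncentrality = difference / [SD × √(1/n₁ + 1/n₂)], with n₁ + n₂ − 2 degrees of freedom.

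For 10 v 10: 13.2 / (10 × √0.2) = 13.2 / 4.472 = 2.952 on 18 df. Power is 79.7%, which agrees with the stated 80%.

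**Step 3. Power if month-6 ABGs are lost.** The documents give no stop rate, so the numbers lost are assumed.

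| Analysed | Noncentrality (df) | Power at 13.2 mmHg | Difference for 80% power |
|---|---|---|---|
| 10 v 10 | 13.2/4.472 = 2.952 (18) | 79.7% | 13.25 mmHg |
| 9 v 10 | 13.2/4.595 = 2.873 (17) | 77.3% | 13.66 mmHg |
| 8 v 10 | 13.2/4.743 = 2.783 (16) | 74.3% | 14.16 mmHg |
| 9 v 9 | 13.2/4.714 = 2.800 (16) | 74.8% | 14.07 mmHg |
| 8 v 8 | 13.2/5.000 = 2.640 (14) | 69.0% | 15.07 mmHg |

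If each letrozole subject had a 5%, 10%, 20% or 30% chance of being stopped and losing the ABG (assumed), the chance of losing at least one of 10 is 1 − (1 − p)¹⁰ = 40%, 65%, 89% or 97%. Power averaged over the number lost is 78.4%, 77.0%, 73.7% or 69.7%. These figures measure precision only. Bias is additional, and neither its size nor its direction can be derived from the documents.

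**Step 4. Power if the subjects are kept but are off drug.** Letrozole's half-life is 2 days (1.3), and the documents do not say how fast AaPO2 reverts. Suppose k of 10 letrozole subjects keep a fraction f of the 13.2 mmHg effect. The mean difference is 13.2 × [1 − k(1 − f)/10]. Power is by simulation (300,000 trials, 10 v 10).

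| k | f | Mean difference | Power, kept | Power, dropped (Step 3) |
|---|---|---|---|---|
| 1 | 0 | 11.88 mmHg | 68.1% | 77.3% |
| 1 | 0.5 | 12.54 mmHg | 74.9% | 77.3% |
| 2 | 0 | 10.56 mmHg | 55.1% | 74.3% |
| 2 | 0.5 | 11.88 mmHg | 69.7% | 74.3% |
| 1 or 2 | 1 | 13.20 mmHg | 79.7% | 77.3% or 74.3% |

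Keeping these subjects gains power only if most of the effect persists off drug. The dropped column assumes that the loss is unrelated to outcome, which is the assumption in doubt.

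**The case against.** Section 9.4 is the section written for withdrawal. It is specific, it gives a closed list for compulsory withdrawal from procedures, and it covers investigator decisions. Section 9.6.1 is one sentence about safety monitoring and says nothing about assessments or analysis, so it most naturally means stopping study drug. For the ABG to be lost, 9.6.1 must override 9.4, and the follow-up sentence in 4.6.1 must be read as cancelling scheduled visits when it could mean only that there is no extra follow-up. Section 4.6.2 also leans towards collecting data. On this view the design is already right and one sentence is loosely worded.

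Two further points are fair. Exclusion from the primary test comes from the completers-only rule in 8.4.5, which applies to any missing month-6 ABG and should not be counted twice. The power figures do not argue for the change, because by Step 4 it can cost power. Reporting stops by arm also overlaps with the CONSORT summaries in 8.3 and the recording of withdrawal reasons in 9.4.

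Most of this stands as qualification. The 9.4 reading is probably the intended one, and the harm is conditional. But a site must act on the words it has: 9.6.1 is mandatory, 4.6.1 supports the literal reading, 4.6.2 does not require the ABG, and no text ranks them. In a 20-subject trial one misapplied rule removes a tenth of an arm from the primary comparison.

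**Conclusion.** The concern holds: it should be corrected, with medium confidence. The contradiction is certain; its consequence is conditional. If 9.4 is followed, the ABG is obtained and nothing is lost. If 9.6.1 and 4.6.1 are followed literally, the subject leaves the primary test for a reason that may depend on treatment, against the stated intent-to-treat principle.

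The loss of precision would be modest: 2.4 points of power for one subject in one arm (79.7% − 77.3%) and 10.7 points for two in each arm (79.7% − 69.0%). This assumes SD 10, a difference of 13.2 mmHg and assumed numbers lost. The more important risk is bias, which cannot be quantified here. The argument for the change is consistency and a complete randomised comparison.

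**What to change.** - **9.6.1:** say that these subjects stop study drug and continue all scheduled assessments, including the month-6 ABG, as in 9.4 and 8.4.5.
- **4.6.1:** change the follow-up sentence to exclude only clinical follow-up beyond the scheduled study assessments. Make the safety-and-tolerability sentence state that these subjects also stay in the AaPO2 comparison.
- **8.4.5:** state that subjects who stop drug stay in the primary AaPO2 comparison whenever a month-6 ABG is available, in line with 8.4.1 and 8.6.
- **Reporting:** show stops under 9.6.1 by arm within the disposition summary already planned in 8.3.

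The cost is a few sentences. No procedure is added, because the month-6 ABG is already in the visit schedule. The downside is possible dilution from off-drug values, as in Step 4, and it should be accepted knowingly. Which side effects should stop the drug is a clinical decision for the investigators and is not affected.

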9.7 Confidentiality of Study Data

Information about study subjects will be kept confidential and managed according to the requirements of the Health Insurance Portability and Accountability Act of 1996 (HIPAA). Those regulations require a signed subject authorization informing the subject of the following:

- What protected health information (PHI) will be collected from subjects in this study
- Who will have access to that information and why
- Who will use or disclose that information
- The rights of a research subject to revoke their authorization for use of their PHI.

In the event that a subject revokes authorization to collect or use PHI, the investigator, by regulation, retains the ability to use all information collected prior to the revocation of subject authorization. For subjects that have revoked authorization to collect or use PHI, attempts should be made to obtain permission to collect at least vital status (long term survival status that the subject is alive) at the end of their scheduled study period.

10 Quality Control and Data Handling

Design strategies and monitoring activities throughout the study will ensure the integrity and high quality of the data. Design strategies include randomization of treatment assignment, masking, and training and certification of personnel. The rigorous monitoring program includes data queries and performance monitoring over the time of the trial.

10.1 Personnel Training

Prior to randomization of the first subject in the study protocol, the PI will ensure that the staff has completed appropriate training and that all documentation including IRB approval is completed and available. The purpose of training is to ensure that study personnel are carrying out the protocol in a consistent way and adhering to good clinical practice guidelines. Staff will have current Human Subjects Training Certification on file. Before enrollment begins, study coordinators and research assistants who will perform the outcome assessments will be trained in all procedures, including completion of the web-based database.

The PI and research staff will constitute the first line of monitoring of the safety of the human participants. Surveillance for AEs will consist of questioning subjects about potential AEs at every study contact, having subjects report any AE to the study team, and having subjects undergo vital sign checks and physical exams during each study visit. Laboratory values will be performed at selected visits and checked.

All study personnel are required to read the consent form and the protocol.

10.2 Data Quality

The PI will perform continuous monitoring of data quality and completion of CRFs.

On-site audits of each enrollment site will be conducted by the PI and study coordinator staff when 2-4 subjects are enrolled at the site. During these visits, the staff reviews all subjects' eligibility criteria, primary end point, SAEs, and a random sample of at least 10% of database forms against source documents to ensure that the information on the forms is complete and consistent with the source documents. Confirmation of missing visits and documentation will be performed, as will the recording of the disposition of participants who complete or exit the study. All consent forms and screening logs will be audited. Finally, the site PI reviews the reporting, documentation and follow-up of SAEs to assure that these events were handled according to required study procedures.

10.3 Source Documents

Source data is all information, original records of clinical findings, observations, or other activities in a clinical trial necessary for the reconstruction and evaluation of the trial. Source data are contained in source documents. Examples of these original documents, and data records include: hospital records, clinical and office charts, laboratory notes, memoranda, subjects' diaries or evaluation checklists, pharmacy dispensing records, recorded data from automated instruments, copies or transcriptions certified after verification as being accurate and complete, microfiches, photographic negatives, microfilm or magnetic media, x-rays, subject files, and records kept at the pharmacy, at the laboratories, and at medico-technical departments involved in the clinical trial.

10.4 Case Report Forms

The study case report form (CRF) is the primary data collection instrument for the study. All data requested on the CRF must be recorded. All missing data must be explained. If a space on the CRF is left blank because the procedure was not done or the question was not asked, write "N/D". If the item is not applicable to the individual case, write "N/A". All entries should be printed legibly in black ink. If any entry error has been made, to correct such an error, draw a single straight line through the incorrect entry and enter the correct data above it. All such changes must be initialed and dated. Do not erase or use "white-out" for errors. For clarification of illegible or uncertain entries, print the clarification above the item, then initial and date it. If the reason for the correction is not clear or needs additional explanation, neatly include the details to justify the correction. Additional data will be stored in REDCAP, a secure web-based database.

10.5 Data Management

We will use REDCap, a validated secure HIPAA compliant database for data management.

Data Processing

As this is a two center study, all data collected will be entered into REDCAP by a study coordinator or co-investigator.

Data Security and Confidentiality

Research data will be stored with a code rather than any patient identifiers to protect patient confidentiality. All protected health information and the key to link patient identifiers to the sample code will be contained in REDCap, a secure web-based HIPAA compliant database that will only be accessible by study personnel authorized by the investigator.

Data Quality Assurance

Double data entry will be used and random data will be cross-checked and validated by the PI with source document verification.

Data Clarification Process

Data will be cross-checked with CRFs and the EMR for any data queries.

10.6 Audit and Inspection

Inspections by regulatory health authority representatives [i.e., FDA and IEC(s)/IRB(s)] are possible.

10.7 Archiving

Essential documents shall be archived safely and securely in such a way that ensures that they are readily available upon authorities' request.

Patient (hospital) files will be archived according to local regulations and in accordance with the maximum period of time permitted by the hospital, institution or private practice.

10.8 Records Retention

The sponsor-investigator will maintain records and essential documents related to the conduct of the study. These will include subject case histories and regulatory documents.

The sponsor-investigator will retain the specified records and reports for;

1. Up to 2 years after the marketing application is approved for the drug; or, if a marketing application is not submitted or approved for the drug, until 2 years after shipment and delivery of the drug for investigational use is discontinued and the FDA has been so notified. OR
2. As outlined in the Mayo Clinic Research Policy Manual –“Retention of and Access to Research Data Policy” http://mayocontent.mayo.edu/research-policy/MSS_669717 whichever is longer

11 Ethical Considerations

This study is to be conducted accordance with applicable US government regulations and international standards of Good Clinical Practice, and applicable institutional research policies and procedures.

This protocol and any amendments will be submitted to a properly constituted IRB in agreement with local legal prescriptions for formal approval of the study conduct. The decision of the IRB concerning the conduct of the study will be made in writing to the investigator and a copy of this decision will be provided to the NIH before commencement of this study.

All subjects for this study will be provided a consent form describing this study and providing sufficient information for subjects to make an informed decision about their participation in this study. This consent form will be submitted with the protocol for review and approval by the IRB for the study. The formal consent of a subject, using the IRB-approved consent form, must be obtained before that subject undergoes any study procedure. The consent form must be signed by the subject, and the investigator-designated research professional obtaining the consent.

12 Study Finances

